After the acute inflammatory phase (six months following disease onset), disease activity was systematically evaluated based on both clinical and subclinical signs. Specifically, clinical signs included anterior chamber cells (ACC) of at least 1+ cells, exudative retinal detachment, and macular edema confirmed on FA and/or OCT. Visual acuity measurement with a Snellen chart was converted to LogMAR values. Subclinical

signs are those detected exclusively in posterior segment imaging (PSI) and included optic disc leakage/hyperfluorescence (ODH) and/or perivasculär leakage on FA; hypofluorescent DD on ICGA; and, increase of at least 30% in subfoveal choroidal thickness (CT) in two consecutive EDI-OCT examinations. Perivasculär leakage was observed as an increase in hyperfluorescence around retinal vasculature over time on FA exam at midperiphery. Isolated subclinical signs of activity did not infer change in treatment schedule, whereas clinical signs led to either an increase in a daily oral prednisone dosage of 0.2 mg/kg (up to at least 0.5 mg/kg/day) or the introduction of non-steroidal IMT (i.e., azathioprine, cyclosporine, or mycophenolate mofetil). Any intolerance to corticosteroid also determined a switch in treatment to non-steroidal IMT. Based on the predefined protocol, the term “flare” was used to describe the appearance or worsening of inflammatory signs observed at least sixth months after disease onset. During the 24-month follow-up period, the presence of ocular complications (i.e., cataract [6], ocular hypertension/glaucoma [7,8], choroidal neovascularization (CNV) [9], or SGF) was recorded. Cataract was defined as any lens opacification greater than nuclear or cortical 2+/4 or subcapsular 1+/4 [6]. Ocular hypertension was defined as an intraocular pressure (IOP) above 21mmHg [7,8]. The CNV membrane was diagnosed when increasingly localized hyperfluorescence at the posterior pole is detected on FA or a hyperreflective subretinal lesion associated with sub or intraretinal fluid on OCT.

The main outcomes measures included clinical and subclinical flares, presence of sunset glow fundus, and ff-ERG results from 12 to 24 months of follow-up.

STATISTICAL ANALYSIS PLAN WITH RESULTS INFORMATION

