For the comparison of qualitative and quantitative data between the stable ERG and worsening ERG groups, the Fisher exact test and Mann Whitney test, respectively, was used (**Tables 2 and 3**). Furthermore, Kappa statistics was used to test interrater reliability between subnormal ERG and SGF. P values ≤ 0.05 were considered statistically significant. Generalized estimated equations (GEE) were used for analyzing binary ocular data. (**Tables 2 and 3**) Data analysis and statistical tests were conducted using SPSS 20.0 (SPSS Science, Chicago, IL, USA).

Table 2 Electrotoretinogram results at 12 and 24 months (median value) and variation between 24 and 12 months in patients with Vogt-Koyanagi-Harada disease and controls

Parameters ^a	Controls (n = 61 eyes)	Patients (n = 24 eyes)				ERG-based groups						p ^d	
					p ^c	Stable (n = 17 eyes)			Worsening (n = 7 eyes)				
		T12	T24	T24-T12 ^b		T12	T24	T24-T12 ^b	T12	T24	T24-T12 ^b		
Scotopic													
^b Amplitude (μV)	211 (114–366)	201 (104–352)	189 (130–380)	8 %	0.504	192 (104–352)	210 (130–380)	9.5 %	231 (112–300)	161 (134–183)	–32.9 %	0.006	
^b Latency (ms)	77 (70–86)	89 (78–100)	89 (75–99)	–0.4 %	<0.001	90 (78–100)	89 (75–99)	–0.6 %	87 (81–92)	148 (120–262)	2.3 %	0.319	
Maximum scotopic													
^a Amplitude (μV)	300 (211–440)	210 (134–336)	189 (120–317)	–1.5 %	<0.001	203 (134–336)	224 (166–317)	7 %	215 (157–330)	148 (120–262)	–21.4 %	<0.001	
^a Latency (ms)	22 (18–23)	23 (19–25)	23 (20–55)	–0.6 %	0.008	23 (22–25)	23 (22–55)	–1.3 %	23 (19–24)	24 (20–54)	5.2 %	0.295	
^b Amplitude (μV)	510 (348–789)	508 (328–728)	484 (336–769)	–1.4 %	0.164	507 (328–728)	528 (355–769)	2.8 %	546 (398–597)	404 (336–540)	–10.8 %	0.001	
^b Latency (ms)	44 (36–50)	50 (44–62)	50 (41–55)	–2.3 %	<0.001	50 (44–62)	50 (46–55)	–1.3 %	49 (45–50)	46 (41–54)	–3.3 %	<0.001	
Oscillatory potential (μV)	121 (92–228)	92 (48–272)	114 (35–259)	0.7 %	0.215	95 (48–272)	135 (46–259)	5.9 %	88 (71–119)	55 (35–130)	–47.1 %	0.168	
Photopic													
^a Amplitude (μV)	50 (34–89)	42 (23–63)	43 (23–66)	–1 %	0.004	42 (23–60)	44 (23–66)	0 %	33 (25–63)	33 (24–52)	–5 %	0.328	
^a Latency (ms)	15 (14–17)	16 (14–17)	16 (14–17)	–2.2 %	0.005	16 (15–17)	16 (14–17)	–2.5 %	16 (14–17)	16 (14–17)	3.7 %	0.723	
^b Amplitude (μV)	227 (106–367)	202 (87–312)	186 (111–345)	–1.4 %	0.025	190 (113–312)	209 (147–345)	2.4 %	218 (87–236)	176 (111–190)	–13.6 %	0.139	

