^b Latency (ms)	31 (27–34)	31 (29–35)	31 (29–33)	–2.6 %	0.263	31 (29–35)	30 (29–33)	–1.8 %	32 (31–33)	31 (29–32)	–2.8 %	0.628	
Flicker 30 Hz	68 (42–122)	52 (24–89)	54 (29–85)	0.3 %	<0.001	53 (32–89)	55 (37–85)	6.2 %	52 (24–81)	36 (29–67)	–6.9 %	0.189	

^a ERG measures represented as median; ERG: electrotoretinography, Mann-Whitney test between ERG-based groups; ^b difference, in percentage, between values observed at 24 and 12 months was calculated for each patient and the median value is here represented; ^c p value comparing controls × patients at 24 months—generalized estimated equation with normal distribution and logarithmic link function, supposing an interchangeable correlation matrix between the eyes; ^d p value comparing T24–12 months between stable and worsening ff-ERG groups—generalized estimated equation with normal distribution and logarithmic link function, supposing an interchangeable correlation matrix between the eyes

Table 3 Electroretinogram-based groups of patients with Vogt-Koyanagi-Harada disease and their clinical characteristics

	ERG-stable group	ERG-worsening group	p
N (eyes)	17	7	
Age, years, median (range)	32 (15–42)	22 (21–67)	0.864 ^a
Interval to treatment start, days, median (range)	21 (3–51)	17 (7–33)	0.727 ^a
Visual acuity at M1(logMAR), median (range)	0.3 (0–2)	0.1 (0–0.7)	0.433 ^b
Choroidal thickness at M1, μm , median (range)	545 (308–904)	635 (303–911)	0.001 ^c
Inflammatory signs, eyes (%)			
Anterior chamber cells fluctuation	8 (47.1)	0 (0)	0.054 ^d
Choroidal thickness fluctuation, eyes (%)	8 (47.1)	4 (57.1)	0.022 ^e
Dark dots fluctuation ^o			
None	0 (0)	2 (28.6)	0.478 ^f
One	12 (70.6)	2 (28.6)	
Two	2 (11.8)	3 (42.8)	
Three	3 (17.6)	0 (0)	
Perivasculär leakage	9 (52.9)	4 (57.1)	0.936 ^e
Ocular complications, eyes (%)			
Cataract	5 (29.4)	0 (0)	0.272 ^d
Ocular hypertension	7 (41.2)	5 (71.4)	0.983 ^e
Sunset glow fundus	8 (47.1)	2 (28.6)	0.988 ^e
Neovascularization	2 (11.8)	1 (14.3)	0.853 ^e
Fibrosis	4 (23.5)	2 (28.6)	0.846 ^e
Treatment, patients (%)			
Additional NS immunosuppression	5 (55.6)	1 (33.3)	>0.999 ^d
Prednisone increment**	6 (66.7)	2 (66.7)	>0.999 ^d

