^aMann-Whitney; ^bgeneralized estimated equation with normal distribution and logarithmic link function, supposing an interchangeable correlation matrix between the eyes; ^cgeneralized estimated equation with normal distribution and identity link function, supposing an interchangeable correlation matrix between the eyes; ^dFisher exact test; ^egeneralized estimated equation with binomial distribution and logit link function, supposing an interchangeable correlation matrix between the eyes; ^fgeneralized estimated equation with Poisson distribution and identity link function supposing an interchangeable correlation matrix between the eyes; ^oincrease in the number of DD by region, whether in the posterior pole or in each quadrant, followed by a diminishment. Objectively was defined as a variation in the final score between two different points in time ≥ 0.5 (Tugal-Tutkun et al., 2010). NS, non-steroidal; **two patients that received increment in prednisone dose presented one eye in stable and one eye in worsening groups

REFERENCES

- [1] R. W. Read et al., “Revised Diagnostic Criteria for Vogt-Koyanagi-Harada Disease: Report of an International Committee on Nomenclature,” *Am. J. Ophthalmol.*, vol. 131, pp. 647–652, 2001.
- [2] F. T. da Silva, C. E. Hirata, E. Olivalves, M. K. Oyamada, and J. H. Yamamoto, “Fundus-based and electroretinographic strategies for stratification of late-stage Vogt-Koyanagi-Harada disease patients. *Am J Ophthalmol* 148(6):939–945
- [3] I. Tugal-Tutkun, C. P. Herbort, and M. Khairallah, “Scoring of dual fluorescein and ICG inflammatory angiographic signs for the grading of posterior segment inflammation (dual fluorescein and ICG angiographic scoring system for uveitis),” *Int. Ophthalmol.*, vol. 30, no. 5, pp. 539–52, Oct. 2010.
- [4] D. L. McCulloch et al., “ISCEV Standard for full-field clinical electroretinography (2015 update),” *Doc. Ophthalmol.*, vol. 130, pp. 1–12, 2015.
- [5] E. L. Berson et al., “Natural Course of Retinitis Pigmentosa Over a Three Year Interval,” *Am. J. Ophthalmol.*, vol. 99, no. 3, pp. 240–251, 1985.
- [6] L. T. Chylack, J. K. Wolfe, D. M. Singer, M. C. Leske, M. a Bullimore, and L. Ian, “Opacities Classification,” *Arch. Ophthalmol.*, vol. 111, pp. 831– 836, 1993.

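### Table 3's footnote e p-values do not fit the eye counts (0.022 for 8/17 v 4/7; 0.983 and 0.988 for larger differences) and should be checked and re-run

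*Combined protocol and SAP*

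**What the plan says.** The statistical analysis plan assigns binary eye-level data to GEE and states that "P values ≤ 0.05 were considered statistically significant". Six rows of Table 3 carry footnote e, a generalized "estimated equation with binomial distribution and logit link function, supposing an interchangeable correlation matrix between the eyes". They include "Choroidal thickness fluctuation, eyes", "Ocular hypertension" and "Sunset glow fundus"; the others are perivascular leakage, neovascularization and fibrosis. The first is the only one of the six with p at or below 0.05. Sunset glow is also a named main outcome: the protocol lists "clinical and subclinical flares, presence of sunset glow fundus, and ff-ERG results from 12 to 24 months".

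The text available for review does not give the type of standard error, the scale, the fitted correlation, a convergence check or the pairing of eyes for these rows. Two places bear on the pairing. The rows under "Treatment, patients" have percentages that imply denominators of 9 and 3. Footnote ** says that "two patients that received increment in prednisone dose presented one eye in stable and one eye in worsening groups".

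**The concern.** The same model on the same 24 eyes gives p=0.022 for a 10-point difference (47.1% v 57.1%). It gives 0.983 for a 30-point difference (41.2% v 71.4%) and 0.988 for an 18-point one (47.1% v 28.6%). Allowing for fellow-eye correlation can move p-values either way, but a reversal this large needs an explanation.

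Two readings of the table are at stake. Under the plan's own rule, fluctuation counts as a significant difference between the ERG groups. And a p-value of 0.988 on a main outcome invites the reading that the groups do not differ, although the data are too few to show that.

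**Working it through.** **1. Counts against printed values.** From Table 3, the odds ratios (worsening v stable) are:

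- fluctuation: (4/3)/(8/9) = 1.50
- hypertension: (5/2)/(7/10) = 3.57
- sunset glow: (2/5)/(8/9) = 0.45

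For fluctuation the unpaired SE of the log odds ratio is √(1/8 + 1/9 + 1/4 + 1/3) = 0.905. With an odds ratio of 1.50, p=0.022 (z = 2.29) would need an SE of ln(1.50)/2.29 = 0.18.

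**2. Patients.** 5/0.556 = 9 and 1/0.333 = 3, so 12 patients; 24 eyes then means two each. The 7 worsening eyes = 2 × (patients with both eyes worsening) + (split patients), so the number split must be odd: 1, 3, 5 or 7. Footnote ** reports two. If those two were counted in both columns, there would be 9 + 3 − 2 = 10 patients, or 20 eyes.

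**3. Reproducing the printed p-values.** A binomial-logit GEE with exchangeable correlation was fitted to every arrangement of the published counts over 12 two-eyed patients. One set-up returns all six values: 8 patients both stable, 1 split, 3 both worsening; model-based SE, scale 1, parameter-adjusted correlation, with the correlation capped at an assumed 0.9999 where it reaches its bound. Exactly one arrangement matches in each row, out of 36, 36, 24, 27, 6 and 15.

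| Row | Stable | Worsening | OR, counts | Fisher p | Printed p | Reproduced p | Fitted OR |
|---|---|---|---|---|---|---|---|
| CT fluctuation | 8/17 | 4/7 | 1.50 | 1.00 | 0.022 | 0.0223 | 13.7 |
| Perivascular leakage | 9/17 | 4/7 | 1.19 | 1.00 | 0.936 | 0.9355 | 1.06 |
| Ocular hypertension | 7/17 | 5/7 | 3.57 | 0.37 | 0.983 | 0.9831 | 1.0006 |
| Sunset glow | 8/17 | 2/7 | 0.45 | 0.65 | 0.988 | 0.9878 | 0.9996 |
| Neovascularization | 2/17 | 1/7 | 1.25 | 1.00 | 0.853 | 0.8532 | 1.25 |
| Fibrosis | 4/17 | 2/7 | 1.30 | 1.00 | 0.846 | 0.8458 | 1.25 |

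With 3, 5 or 7 split patients the same set-up returns at most one of the six. Robust SEs reproduce none of 0.022, 0.983 and 0.988 in any layout.

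**4. Fluctuation under the match.** The split patient has the sign in the worsening eye only. The fitted correlation is 0.845, which puts heavy weight on that within-patient contrast: ln(13.7)/1.145 = 2.29, p = 0.022. Without that patient the counts are 8/16 v 3/6, OR 1.00, p = 1.00. With all 12 patients, the robust SE gives p = 0.19.

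**5. Hypertension and sunset glow under the match.** Both eyes of every patient agree, and the uncapped correlation estimate is about 1.1, so the working matrix is not positive definite. Near a correlation of 1 almost all the weight falls on the split patient, whose two eyes agree, and the odds ratio is forced to about 1. The p-value then follows the cap:

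| Cap | Hypertension p | Sunset glow p |
|---|---|---|
| 0.99 | 0.834 | 0.881 |
| 0.999 | 0.947 | 0.961 |
| 0.9999 | 0.983 | 0.988 |
| 0.99999 | 0.995 | 0.996 |

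**6. Re-run.** Each patient's pair of ERG labels is shuffled across patients: 12 × C(11,3) × 2 = 12 × 165 × 2 = 3,960 allocations. With the difference in proportions as the statistic, p is 1.00 for fluctuation, 1.00 for leakage, 0.55 for hypertension, 0.79 for sunset glow, 1.00 for neovascularization and 1.00 for fibrosis.

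The fluctuation value does not depend on the pairing. With 12 affected eyes out of 24, 7 × 12/24 = 3.5 are expected in the worsening group. The observed 4 is as close as a whole number can be, so every allocation is at least as extreme.

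**The case against.** The strongest objection is that the matching layout contradicts the only pairing statement in print: it has one split patient, and footnote ** reports two. Either the footnote or the inference is wrong, and the account of one influential patient depends on which. This stands, and it puts reconciliation first. Four layouts of 13 to 15 patients with two split patients and some single eyes were also tried; none returned the six values under one set-up.

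The two boundary rows are weaker evidence than a six-of-six match suggests. The cap was chosen because it matches, and at that cap those rows also fit other set-ups. Only four rows discriminate. The plan names SPSS 20.0, and the fits were not repeated in it. Part of the document was not available for review, so pairing or interpretation may be given there.

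The permutation p-value depends on the statistic. For fluctuation in the matching layout it is 1.00 with the difference in proportions, 0.23 with the GEE score, and 0.056 to 0.177 with the fitted Wald statistic, the range reflecting allocations that could not be fitted. The difference in proportions gives no extra weight to a within-patient contrast. None of these reaches 0.05, but any choice made now is post hoc and should be labelled so.

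A reader might infer that the fluctuation SE is simply too small, because the residuals give a scale of 1.86. That does not follow: a binary outcome's variance is fixed by its mean, so scale 1 is natural, and 1.86 signals fitted means that miss the observed proportions. Nor is the model-based test inflated in general; its average error rate in this layout is 0.9% to 4.3%.

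**Conclusion.** The printed footnote e p-values are out of line with their counts. The only one at or below 0.05 and the two closest to 1 do not appear to be valid tests. The mismatch itself needs no reconstruction. The mechanism does: it assumes 12 two-eyed patients, one of them split, model-based SEs with scale 1, and a cap of 0.9999 for two rows. Six matches to three decimals make it the likely explanation but do not establish it.

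A reader might go further and conclude that fluctuation is unrelated to ERG worsening, or that the sponsor claimed equivalence for sunset glow. The documents support neither. About 12 patients cannot exclude an association, and the available text does not interpret 0.988 as no difference. Even ignoring pairing, the 95% interval for sunset glow is exp(ln 0.45 ± 1.96 × 0.968) = 0.07 to 3.00. Hypertension and sunset glow stay non-significant on re-analysis; what changes is that values near 1 can no longer suggest similarity.

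**What to change.** 1. From patient-level data, reconcile footnote **, the denominators of 9 and 3, and the 17 + 7 eyes, and report how many patients are split. Check the software output for patient as the cluster, SE type, convergence and a working correlation at its bound.
2. Re-run all six footnote e rows, not only those where every patient is concordant. Use an independence working correlation, so that the odds ratio equals the one from the counts, with patient as cluster. Take the p-value from a patient-level permutation test, with the difference in proportions as the single statistic for every row.
3. Replace the six p-values, print odds ratios with small-sample cluster-adjusted 95% intervals, and state that the re-analysis is post hoc. Suggested footnote e: *GEE, binomial-logit, independence working correlation, patient as cluster; odds ratio with small-sample cluster-adjusted 95% CI; p-value from a post hoc patient-level permutation test of the difference in proportions.*
4. Do not call choroidal thickness fluctuation significant unless it survives, and do not read the sunset glow or hypertension p-values as evidence of no difference.

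The cost is a short re-analysis of existing data and a corrected table. The fluctuation p-value will be less favourable, and the intervals will be wide.

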TRC-50DX (Tokyo, Japan); FA, ICGA and EDI-OCT were performed using Spectralis® HRA+OCT (Heidelberg Engineering, Germany). Fundus findings were graded according to a previously described analytical framework [2]. The development of sunset glow fundus was classified as either present or absent based on the fundus color photography. Imaging examinations were read by two well-trained examiners. In case of instances of disagreement, the senior reader would classify the images and would be responsible for the final decision. The FA and ICGA reading charts were adapted from Tugal-Tutkun et al [3]. Dark dots (DD) were evaluated based on a semi-quantitative score for the posterior pole and each quadrant: sparse and/or faint and numerous and/or pronounced. The total score varies from 0 to 8. Fluctuation was defined as a change in DD quantity (e.g., sparse to numerous or vice versa) according to the Tugal-Tutkun et al score and whether the DD in the posterior pole or in each quadrant [3]. Objectively, DD fluctuation was defined as a final score variation ≥ 0.5 between two different points in time. ff-ERG recordings were performed in accordance with the International Society for Clinical Electrophysiology of Vision guidelines with the RETI-port system (Roland Consult) using ERG-jet electrodes (Universe SA, La Chaux-deFons, Switzerland) [4]. Scotopic ERG responses were recorded after a period of 20 minutes of dark adaptation, and photopic ERG responses were recorded after 10 minutes of light adaptation. The recording sequence was scotopic rod response, scotopic cone–rod combined response, scotopic oscillatory potentials, photopic cone response, and 30-Hz flicker cone response. The normal value limits for each specific ERG response were established at 95% confidence intervals. Amplitude and implicit time of a and b wave of eight averaged stimulus response for each phase were analyzed, and the results were compared with a normative database. The worsening of the ERG parameters was defined as value reduction $> 30\%$ in any scotopic ERG parameter, which needed to be confirmed in two consecutive examinations [5]. ff-ERG scotopic parameters obtained at 12 and 24 months were compared; all included eyes were grouped based on the worsening or stabilization of the scotopic parameters from 12th to 24th month.

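### Table 3's patient-level rows rest on 9 stable and 3 worsening patients, but 7 worsening eyes need at least 4 patients, or 5 by the table's own footnote

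*Combined protocol and SAP*

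**What the plan says.** The protocol's ff-ERG methods form the comparison groups by eye: "all included eyes were grouped based on the worsening or stabilization of the scotopic parameters from 12th to 24th month". Tables 2 and 3 give 17 stable and 7 worsening eyes, 24 in all. The statistical section says that for "the stable ERG and worsening ERG groups, the Fisher exact test and Mann Whitney test, respectively, was used".

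Table 3 then changes unit. Under "Treatment, patients" (%) it prints, stable v worsening:

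- additional non-steroidal immunosuppression: 5 (55.6) v 1 (33.3), Fisher p > 0.999
- prednisone increment: 6 (66.7) v 2 (66.7), Fisher p > 0.999

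Age (p = 0.864) and interval to treatment start (p = 0.727) are compared by Mann-Whitney. Footnote **, attached to the prednisone row, states that two "patients that received increment in prednisone dose presented one eye in stable and one eye in worsening groups". The text supplied gives no patient denominators, and no rule for placing a patient whose eyes fall in different groups.

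**The concern.** A patient is not an eye, and a patient with one stable and one worsening eye has no natural place in a two-column table. The percentages imply a worsening column of 3 patients, which is too few to own 7 worsening eyes.

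A reader will take 55.6% v 33.3% and 66.7% v 66.7% as treatment by ERG course, and the age and interval rows as evidence that the groups were alike. If some patients with a worsening eye sit under the stable heading, or are missing, those readings are not supported. With 3 patients in a column, moving one patient's outcome shifts the percentage by 33 points.

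**Working it through.** **Inputs.** 17 stable and 7 worsening eyes (Tables 2 and 3); the four counts and percentages and the four p values in Table 3's treatment, age and interval rows; the two discordant patients in footnote **.

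**1. Denominators.** 5/9 = 55.6% and 6/9 = 66.7%; 1/3 = 33.3% and 2/3 = 66.7%. A search of denominators up to 79 finds no other fit. The neighbours miss clearly: 5/8 = 62.5%, 5/10 = 50.0%, 1/2 = 50.0%, 1/4 = 25.0%.

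**2. Printed p values reproduced.** Fisher's exact test on 5/9 v 1/3 and on 6/9 v 2/3 gives p = 1.0 each, as printed. The eye-level Fisher rows reproduce at 17 v 7: anterior chamber cells, 8/17 v 0/7, p = 0.054; cataract, 5/17 v 0/7, p = 0.272. So the table was read correctly.

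**3. Age and interval.** With 9 v 3 there are 220 possible rank allocations. The exact two-sided Mann-Whitney p is 190/220 = 0.864 at U = 12 and 160/220 = 0.727 at U = 11, the two printed values. No other split of 4 to 24 patients gives both, and 17 v 7 gives neither. The printed medians and ranges allow these U values: three worsening patients would have ages 21, 22, 67 and intervals 7, 17, 33. This assumes exact p values and no ties.

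**4. Fewest patients with a worsening eye.**

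- From eye counts alone: 7/2 rounded up = 4. Outside a column of 3: 4 − 3 = 1, or 1/4 = 25%.
- With the footnote: two discordant patients supply 2 worsening eyes. The other 7 − 2 = 5 need 5/2 rounded up = 3 patients, so 2 + 3 = 5. Outside: 5 − 3 = 2, or 2/5 = 40%.
- At most 7 patients can own a worsening eye: 7 − 3 = 4 outside, or 4/7 = 57%.

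These bounds assume no patient total and do not need every patient to give two eyes.

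**5. Can a counting rule avoid this?** There are 160 ways to spread 17 stable and 7 worsening eyes over patients giving one or two eyes. Placing each discordant patient in the stable column, the worsening column, both or neither, 59 combinations give 9 v 3. In all 59, 1 to 4 patients with a worsening eye are outside the worsening column (2 to 4 where at least two are discordant). Counting every discordant patient in both columns never works, because the worsening column would then hold every owner of a worsening eye, at least 4.

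If each patient is counted once (9 + 3 = 12 patients, both eyes each), four layouts are possible:

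| Both stable | Discordant | Both worsening | With a worsening eye | Outside worsening column | Fits footnote ** |
|---|---|---|---|---|---|
| 8 | 1 | 3 | 4 | 1 (25%) | no |
| 7 | 3 | 2 | 5 | 2 (40%) | yes |
| 6 | 5 | 1 | 6 | 3 (50%) | yes |
| 5 | 7 | 0 | 7 | 4 (57%) | no |

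The last column asks for exactly two discordant patients with an increment and 8 increments in total. If discordant patients were instead excluded, there would be 13 to 16 patients, of whom 2 to 8 gave one eye.

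**6. Illustration, not an estimate.** Take the 7/3/2 layout with two discordant patients counted as stable (7 + 2 = 9, 2 + 1 = 3), and regroup as no worsening eye (7) v any (5):

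- Prednisone increment, printed as 66.7% v 66.7%, becomes 5/7 = 71.4% v 3/5 = 60.0% (p = 1.0) or 4/7 = 57.1% v 4/5 = 80.0% (p = 0.58).
- Immunosuppression runs from 5/7 = 71.4% v 1/5 = 20.0% (p = 0.24) to 3/7 = 42.9% v 3/5 = 60.0% (p = 1.0).

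In the 6/5/1 layout the lowest p values are about 0.08 for immunosuppression and 0.06 for increment.

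**The case against.** The best defence is that no figure is shown to be wrong. Every treatment percentage and Fisher p value reproduces, and the 7/3/2 layout yields 17 v 7 eyes, 9 v 3 patients and the footnote without any miscount. Groups are defined by eye, so patient rows need some convention, and that convention may be set out in the part of the statistical section removed from the text supplied to us. Footnote ** already discloses discordant eyes for one row. The 9 v 3 basis of the age and interval rows is inferred. No p value in the 12-patient layouts that fit the footnote reaches 0.05, and three patients would support no treatment inference under any rule.

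Much of this stands. The cause is unknown, a missing rule should not be held against the plan, the age and interval reading is an inference, and no changed conclusion is shown. The 25% figure is a floor that sets the footnote aside.

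It does not remove the problem. No rule can fit 7 eyes into 3 patients, so any convention that gives 9 v 3 puts some patients with a worsening eye in the stable column or in neither. The footnote does not say which column its two patients are in, and it is not attached to the other three rows. Describing the convention would explain the 9 v 3 split but leave the comparison as it is.

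**Conclusion.** The concern holds. The treatment rows of Table 3 use 9 and 3 patients and do not compare all patients with a worsening eye against those without. Between 1 of 4 (25%) and 4 of 7 (57%) of patients with a worsening eye are outside the worsening column; if footnote ** is right, between 2 of 5 (40%) and 4 of 7 (57%).

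For the treatment rows this rests only on printed figures, and confidence is high. For age and interval it also rests on exact, tie-free Mann-Whitney p values. Whether the cause is classing each patient by one eye, excluding discordant patients or a miscount cannot be told. Neither the denominators nor the footnote is shown to be wrong.

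The effect on the percentages and p values needs patient-level data. The main outcomes are listed as "The main outcomes measures included clinical and subclinical flares, presence of sunset glow fundus, and ff-ERG results from 12 to 24 months of follow-up"; the four rows here describe treatment, age and interval by ERG group and are not among them. The point should be corrected, but it does not touch the central results.

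**What to change.** From the existing data:

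1. Report how many patients have both eyes stable, discordant eyes, both eyes worsening, and one eye only.
2. Print the patient denominators in Table 3 beside the eye counts.
3. Assign each patient once, by a stated rule that keeps anyone with a worsening eye out of the stable column. Any worsening eye v none would do, as would a separate discordant category.
4. Recount the two treatment rows and rerun Fisher's test. Rerun Mann-Whitney for age and interval on the same classification.
5. Change footnote ** only if the recount shows it to be wrong.

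The cost is a small reanalysis of four table rows, with no new data.
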